Confidentiality will be protected by collecting only information needed to assess study outcomes, minimizing to the fullest extent possible the collection of any information that could directly identify subjects, and maintaining all study information in a secure manner. To help ensure subject privacy and confidentiality, only a unique study identifier will appear on the data collection form. Any collected patient identifying information corresponding to the unique study identifier will be maintained on a linkage file, stored separately from the data. The linkage file will be kept secure, with access limited to designated study personnel. Following data collection subject identifying information will be destroyed 6 years after study completion by deleting the linkage file, consistent with data validation and study design, producing an anonymous analytical data set. Data access will be limited to study staff. Data and records will be kept locked and secured, with any computer data password protected. No reference to any individual participant will appear in reports, presentations, or publications that may arise from the study.

In group meetings with participants, respect for the privacy and confidentiality of other group attendees will be emphasized.

Data and Safety Monitoring

The principal investigator will be responsible for the overall monitoring of the data and safety of study participants. The principal investigator will be assisted by other members of the study staff. A Data Safety and Monitoring Committee, an independent group of experts, will be reviewing the data from this research throughout the study

Reporting of Unanticipated Problems, Adverse Events or Deviations

Any unanticipated problems, serious and unexpected adverse events, deviations or protocol changes will be promptly reported by the principal investigator or designated member of the research team to the IRB and sponsor or appropriate government agency if appropriate.

SAFETY AND MONITORING PLAN

Adverse Event Definitions:

Adverse Event: (AE) For the purposes of this trial an adverse event is defined as any untoward or unfavorable medical occurrence that is temporally associated with the subject's participation in the research, whether or not considered related to the subject's participation in the research.

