Expected Events: In this study, no serious adverse events are expected. Expected adverse events include temporary muscle soreness, temporary joint pain, and temporary increased physical fatigue when starting the exercise regimen or when increasing the exercise. Other expected events include mild discomfort from physical exertion including shortness of breath that improves when ceasing exercise and sweating. In people with asthma, an increase in the need for inhaler use is expected. In people who have a very high baseline seizure frequency, and even in those with less frequent seizures, seizures are reasonably expected to occur during exercise on occasion and certainly will occur during the course of the study. However, seizures that occur consistently with exercise in a single individual is not expected. In addition, it is not expected for participants to have a large

Protocol version:

Template updated 9.24.14

increase in seizure frequency. A small increase would be within the normal fluctuation of seizure frequency in people with epilepsy.

Specifically, the temporal relationship of seizures to exercise will be recorded in the daily study diary. Responses will be reviewed by the study team weekly. In participants who demonstrate an increase in seizure frequency from their baseline weekly frequency consistently over a 4 week period, the temporal relationship to exercise will be further investigated. In those who have increased seizure frequency AND who report a clear temporal association with exercise (seizure occurs during or immediately after exercise in 50% or more of their seizures), participation in the intervention will be halted due to concern for exercise-induced seizure activity.

All other events not listed above will be considered unexpected for the purposes of this trial. The unblinded investigator will be responsible for determining whether an AE is expected or unexpected. An AE will be considered unexpected if the nature, severity, or frequency of the event is not consistent with the risk information previously described for the study intervention.

Adverse Event Classification:

All AEs will be assessed by the study staff for severity and categorized using the criteria described below.

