Serious Adverse Events: (SAE) Any event that results in death, hospitalization or prolongation of a hospitalization, significant or persistent disability, a birth defect or congenital anomaly, or another significant event or problem requiring medical or surgical intervention to prevent one or more of the above.

General Adverse Events:

Mild Adverse Events: Events that require minimal or no treatment and do not interfere with the participant's daily activities.

Moderate Adverse Events: Events result in a low level of inconvenience or concern with the therapeutic measures. Moderate events may cause some interference with functioning.

Severe Adverse Events: Events that interrupt a participant's usual daily activity and may require systemic drug therapy or other treatment. Severe events are usually potentially life-threatening or incapacitating. Of note, the term "severe" does not necessarily equate to "serious".

All adverse events will also have their relationship to study intervention assessed by one of the co-investigators (un-blinded) who will examine and evaluate the participant based on temporal relationship and his/her clinical judgment and categorized into one of the following:

Definitely Related: There is clear evidence to suggest a causal relationship, and other possible contributing factors can be ruled out. The clinical event, including an abnormal laboratory test result, occurs in a plausible time relationship to study intervention administration and cannot be explained by concurrent disease or other drugs or chemicals. The response to withdrawal of the study intervention (dechallenge) should be clinically

plausible. The event must be pharmacologically or phenomenologically definitive, with use of a satisfactory rechallenge procedure if necessary.

Probably Related: There is evidence to suggest a causal relationship, and the influence of other factors is unlikely. The clinical event, including an abnormal laboratory test result, occurs within a reasonable time after administration of the study intervention, is unlikely to be attributed to concurrent disease or other drugs or chemicals, and follows a clinically reasonable response on withdrawal (dechallenge). Rechallenge information is not required to fulfill this definition.

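### The serious adverse event definition has no life-threatening criterion, so such an event that resolves without admission, intervention or lasting disability is not counted as serious

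*Combined protocol and SAP*

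**What the plan says.** Four parts of the protocol's safety text bear on this point.

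- **Serious definition (Adverse Event Classification).** The outcome criteria are "Any event that results in death, hospitalization or prolongation of a hospitalization, significant or persistent disability, a birth defect or congenital anomaly". A further clause adds "another significant event or problem requiring medical or surgical intervention to prevent one or more of the above".
- **Severity grades (same section, under General Adverse Events).** The grades are mild, moderate and severe. Of the top grade the protocol says: "Severe events are usually potentially life-threatening or incapacitating". It then notes that severe "does not necessarily equate to" serious. The serious category and the three grades follow one introductory sentence: "All AEs will be assessed by the study staff for severity and categorized using the criteria described below".
- **Prompt reporting (Reporting of Unanticipated Problems, Adverse Events or Deviations).** "Any unanticipated problems, serious and unexpected adverse events, deviations or protocol changes will be promptly reported". No severity grade triggers a report by itself.
- **Expectedness (Expected Events).** No serious event is expected. Of seizures the protocol says that "seizures are reasonably expected to occur during exercise on occasion and certainly will occur during the course of the study". The general rule is: "An AE will be considered unexpected if the nature, severity, or frequency of the event is not consistent with the risk information" already described for the intervention.

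**The concern.** The protocol recognises that some events may threaten life, but it says so only in a severity grade placed outside the serious category. An event that put a participant at immediate risk of death and then passed need not meet any serious criterion.

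The label matters because it largely decides onward reporting. The adverse event trigger requires an event to be both serious and unexpected. Since no serious event is expected, an event classed as serious would ordinarily be unexpected too. Seriousness is thus in effect the deciding condition.

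Participants have active epilepsy and walk at home or wherever they choose. A near-fatal event is one that the IRB and the designers of a larger trial would want counted as serious. At stake are the completeness of the serious event count and the prompt reporting of such an event once it is known.

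**Working it through.** No arithmetic tests the claim, because it depends on no rate, sample size or error level. The check is to take a life-threatening event that the participant survives through the rules as written.

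**Step 1: is it serious?**

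| Course of the event | Criterion met | Serious? |
|---|---|---|
| Admitted, or an existing stay prolonged | Hospitalization | Yes |
| Not admitted, but intervention needed to prevent death or another listed outcome | Intervention clause | Yes |
| Not admitted, no such intervention, lasting or significant disability | Disability | Yes |
| Not admitted, no such intervention, no such disability | None | No |

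Only the last row is a gap. The protocol uses the term life-threatening nowhere outside the Severe grade, so no other passage closes it.

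**Step 2: is a last-row event promptly reported?** The trigger "Any unanticipated problems, serious and unexpected adverse events, deviations or protocol changes will be promptly reported" has four parts.

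- *Serious and unexpected adverse event.* This fails, because the event is not serious. Expectedness cannot rescue it. A self-terminating arrhythmia is not on the expected list and so is unexpected. An unusually dangerous seizure may become unexpected under the severity part of the rule. Neither becomes serious as a result.
- *Unanticipated problem.* This is possible and does not require seriousness. The protocol does not define the term, so the outcome depends on judgement.
- *Deviation* and *protocol change.* Neither applies to a medical event as such.

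**Step 3: what would a life-threatening criterion change?** The last row becomes serious. As no serious event is expected, the event would ordinarily also be unexpected, and so promptly reportable once staff know of it.

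**Step 4: what would it not change?** Adverse Event Tracking sets collection by type of event, not by seriousness. Worsening seizure frequency, falls and injuries go into the diary, which is returned daily; the study team reviews it weekly. Other events are asked about at Visits 2 to 4, scheduled at Weeks 4, 16 and 28, which are 16 − 4 = 12 and 28 − 16 = 12 weeks apart. Those intervals are the same with or without the new criterion.

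**Step 5: does the case report form separate the two judgements?** Among the items that Adverse Event Tracking says will be collected are severity and relationship to the intervention. Seriousness is not named. The list is introduced as what the form includes, so this does not prove that the item is absent, but the text does not show a separate judgement.

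**The case against.** The strongest reply is that the existing text leaves little uncovered, and several stronger readings do not hold.

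- **A reader might infer that any life-threatening event without hospitalization escapes.** It does not. The intervention clause covers events treated to prevent death or another listed outcome. This stands, and it limits the gap to the last row of the table.
- **A reader might infer that such an event can enter only the general adverse event record.** The unanticipated-problem route is separate and could catch some of these events. This stands in part: the route exists, but it is undefined and does not put the event in the serious count.
- **A reader might infer that the gap delays reporting by up to 12 weeks.** That interval comes from the visit schedule and applies whatever the label. Seizures, falls and injuries reach staff through the diary. Coaching contacts and the control arm's calls every two weeks may bring others to light. The delay should not be attributed to this definition.
- **A reader might infer from Management of Seizures that life-threatening events usually pass untreated.** That section says that most seizures need no emergency care. It describes ordinary seizures and is no evidence about life-threatening ones.
- **A reader might cite the threefold risk of sudden cardiac death in the Background.** Death is already the first serious criterion, so that figure does not measure the gap.
- **A reader might infer that a severe event can never be serious.** The protocol says only that the two are not necessarily the same. The heading is awkward, but it is not an exclusion.

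The independent committee reviews data throughout the study, which helps oversight. The protocol describes no duty to send it life-threatening events promptly, so its existence does not replace the criterion.

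**Conclusion.** The point holds in a limited form. As written, a life-threatening event that ends without admission, qualifying intervention or lasting disability is not a serious adverse event. Once known, it is promptly reported only if judged an unanticipated problem. The effect is on classification, the serious event count and onward reporting. Detection is unaffected, and no feasibility endpoint or planned analysis depends on it.

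The size cannot be put as a number, because the documents give no rate for such events. With up to 40 participants the number is probably small and may be zero. The case for acting is that the change is cheap and each such event would matter.

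The conclusion assumes that staff apply the definition as written and that no separate criterion appears in the case report form or the committee's working papers, which are not among the documents supplied.

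**What to change.** 1. Add to the serious criteria in Adverse Event Classification: *is life-threatening (the participant was at immediate risk of death when the event occurred)*.
2. Reword the Severe grade so that it describes intensity only, and state that severity and seriousness are judged separately for every event.
3. Carry both changes into the case report form, as a seriousness item distinct from the severity grade, and into the committee's listings.

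The cost is a phrase in the definition, a reworded grade and matching edits to the form and listings, with possibly a few more prompt reports. The change does not touch the intervention, clinical management, the endpoints or the analysis.

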- The study intervention is simple and the weekly step goal is clearly explained to the participant.
- The weekly step goal is individualized, and is created each week during a 1:1 session with the coach while taking into account the participant's individual barriers.
- Participants will be encouraged to seek social support from family and friends and walk with family and friends when able.
- The intervention period is relatively short (only 12 weeks).
- Participants in the control group will be given a personalized physical activity plan if they complete the study
- All participants will be compensated \$50 per visit (4 visits; for total of \$200/participant) to help cover the costs of transportation, parking, and any time away from employment for each research visit.
- Eligibility criteria are designed to exclude participants in poor physical or emotional health for whom adherence may be challenging.
- Study appointment reminders will be given to all participants. Reminders to complete the study diary will be given daily.
- For in-person study visits, the participant will be contacted 1-3 days prior to remind them and confirm the appointment.
- The group coaching format will enhance social support, participant engagement, and add additional resources to help with troubleshooting barriers. When available, a patient-stakeholder will join the coaching session to provide additional social support.

Strategies to support retention:

- Participants in the control group will be given the opportunity to receive a personalized physical activity program if they complete the study.
- Participants will be compensated \$50 per study visit V1-V4
- Study appointment reminders will be given to both groups.

BLINDING

Due to the nature of the intervention, participants will not be blinded as to whether they are in the intervention or control group.

The final analysis of activity data and heart rate variability (HRV) will also be performed by blinded assessors. An unblinded investigator or sub-investigator will gather the data and de-identify the information such that those processing the data will not be privy to which arm is which. The PI will not be blinded in this pilot feasibility study, in order to best track adherence and fidelity and help troubleshoot unexpected barriers.

FOLLOW-UP VISITS

Visit 3, Week 16 End of Intervention:

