Efficacy Questionnaire (EXSE)[51], Exercise Goal Setting Questionnaire (EGS)[52], and Multidimensional Expectations for Exercise Scale (MOEES)[53]. These will be given in person at Visits 1 and 3 and remotely via redcap survey at Visit 4.

2.

v. Effects on physical function

1. Autonomic tone: Heart rate variability (HRV)

a. Heart Rate Variability (HRV) measurement: Continuous heart rate will be recorded while the participant is breathing normally in seated position for 10 minutes using Faros 180 heart rate monitor (Bittium Corporation, Oulu, Finland)[54]. Beat to beat intervals (RRI) files will be generated at 1000 Hz via the data acquisition software. The files will be analyzed with Nevrokard HRV software (by Nevrokard Kiauta, d.o.o., Izola, Slovenia). The recordings will be visually inspected to ensure data quality (dropped beats or gross motion artifacts are excluded) and the first 5 minutes of usable tracings will be analyzed. We will obtain measures of HRV in the frequency domain and these measures will be integrated over specified frequency ranges (LF: 0.04-0.15 Hz; HF: 0.15-0.4 Hz). Power of RRI spectra in LF, HF range (LFRRI and HFRRI) will be calculated in normalized units and the ratio of LFRRI/HFRRI will be used as a measure of sympatho-vagal balance. We will also calculate the standard deviation of normal-to-normal interval (SDNN) and the root mean square of successive differences (RMSSD) indexes, given their established study in PWE.[11, 12]

2. Cardiorespiratory Fitness:

a. Maximum oxygen uptake (VO₂ max)

i. Cardiopulmonary exercise test using a modified Balke protocol[55, 56] on a treadmill

b. 6-minute walk test (6MWT)

Participants will undergo a 6 minute walk test at Visits 1 and 3, according to established guidelines[57]. This is a cost-effective and well-documented field test for assessing functional exercise capacity and response to medical interventions in diverse patient groups, and predicts cardiorespiratory fitness among healthy people[58].

3. Sleep:

a. Nightly average total sleep time (TST): will be collected from the Garmin activity tracker

b. Sleep quality will be assessed via the Pittsburgh Sleep Quality Index (PSQI)

c.

Analytical Plan

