Potentially Related: There is some evidence to suggest a causal relationship (e.g., the event occurred within a reasonable time after administration of the trial medication). However, other factors may have contributed to the event (e.g., the participant's clinical condition, other concomitant events). Although an AE may rate only as "possibly related" soon after discovery, it can be flagged as requiring more information and later be upgraded to "probably related" or "definitely related", as appropriate.

Unlikely to be related: A clinical event, including an abnormal laboratory test result, whose temporal relationship to study intervention administration makes a causal relationship improbable (e.g., the event did not occur within a reasonable time after administration of the study intervention) and in which other drugs or chemicals or underlying disease provides plausible explanations (e.g., the participant's clinical condition, other concomitant treatments).

Not Related: The AE is completely independent of study intervention administration, and/or evidence exists that the event is definitely related to another etiology. There must be an alternative, definitive etiology documented by the clinician.]

Adverse Event Tracking:

Adverse Events that are of special interest for this study will be actively tracked. These include worsening of seizure frequency, falls, and injuries. These will be specifically recorded by the participant in their study diary, which will be returned electronically daily.

All other adverse events will be passively collected at each study visit (visits 2-4) by asking "have you had any health problems since your last visit?"

All AEs will be captured on the appropriate case report form (CRF). Information to be collected includes event description, time of onset, clinician's assessment of severity, relationship to study intervention (assessed only by those with the training and authority to make a diagnosis), and time of resolution/stabilization of the event. All AEs occurring during the study must be documented appropriately regardless of relationship.

Any medical condition that is present at the time that the participant is screened will be considered as baseline and not reported as an AE. However, if the study participant's condition deteriorates at any time during the study, it will be recorded as an AE.

Management of Suicidal Ideation:

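### Adverse-event relatedness and expectedness are judged only against the study intervention, so the relatedness field cannot separate harm from the exercise tests from harm unconnected to the research.

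*Combined protocol and SAP*

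**What the plan says.** Adverse Event Definitions takes a broad view of what counts as an event: one "temporally associated with the subject's participation in the research, whether or not considered related to the subject's participation in the research".

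The grading is narrower. Adverse Event Classification says "All adverse events will also have their relationship to study intervention assessed by one of the co-investigators (un-blinded"), and all five categories are framed around that one relationship. The case report form items under Adverse Event Tracking repeat it: "relationship to study intervention (assessed only by those with the training and authority to make a diagnosis"). *Not Related* applies when "The AE is completely independent of study intervention administration, and/or evidence exists that the event is definitely related to another etiology", and the clinician must then document a definitive alternative cause. *Unlikely* names other drugs, chemicals or underlying disease as the alternatives. No category mentions a study procedure. Under Expected Events, expectedness is likewise judged against the risk information for the study intervention.

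The protocol does not formally define the study intervention. Strategies to support adherence uses the term for the step-goal program: "The study intervention is simple and the weekly step goal is clearly explained to the participant".

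Both arms also undergo procedures outside that program. The Outcome Measures section lists a "Cardiopulmonary exercise test using a modified Balke protocol" on a treadmill, which the visit schedule marks at Visits 2 and 3 with no restriction by arm. The 6-minute walk test is at Visits 1 and 3. Controls receive no exercise program during the 12 weeks.

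**The concern.** An event can arise from the walking program, from a study procedure, or from neither. The relatedness field asks only about the first, so the second and third share a code. In a study of physical exertion, the procedures most likely to cause harm are themselves exertional, and their after-effects resemble those of the program: the protocol lists soreness, joint pain, fatigue and breathlessness as expected effects of exercise.

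The study is meant to inform a larger trial. Its investigators will want to know whether any harm came from the program, which would be kept, or from the exercise test, which could be changed. A summary by relatedness, whether for the monitoring committee or for publication, would not answer that from the coded field.

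**Working it through.** The plan gives no figure to reproduce. The check has three parts: a reading of the categories against plausible cases, a look at when events are elicited, and a count of tests.

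**1. Which code fits?**

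- *Control, hurt on the treadmill at Visit 2 or 3.* The event is independent of the program and has a definite other cause. Both parts of *Not Related* are met. *Unlikely* fits poorly, since a procedure is not among its named alternatives.
- *Either arm, hurt in the Visit 1 walk test or the Visit 2 treadmill test.* The program has not begun; a note to the schedule requires that a postponed treadmill test still precede the intervention period. For immediate harm, *Not Related* again fits best.
- *Arm 1, soreness or joint pain after a Visit 3 test.* The test and the program are both plausible causes. The field records only the assessor's view of the program.

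**2. When is the event elicited?** The study diary actively tracks worsening seizures, falls and injuries. Everything else is collected passively at Visits 2 to 4 by a question about health problems since the previous visit. The nominal weeks are 0, 4, 16 and 28, and batched enrollment may stretch them.

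- Visit 1 walk test: next asked at Visit 2, 4 − 0 = 4 weeks later, before the program.
- Visit 2 treadmill test: next asked at Visit 3, 16 − 4 = 12 weeks later, after the whole program in arm 1.
- Visit 3 tests, for effects appearing after the visit: next asked at Visit 4, 28 − 16 = 12 weeks later. By then arm 1 has been encouraged to keep walking and, according to the Visit 3 text, controls have been offered a personalized program.

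**3. How many tests?** Inputs: up to 40 participants at 2:1 (Sample Size); two treadmill tests and two walk tests each (schedule). Assume that all 40 are randomized and complete everything.

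- Split: 40 × 2/3 ≈ 27 in arm 1 and 40 × 1/3 ≈ 13 controls.
- Exertional tests: 40 × 4 = 160.
- Before any program: 40 × 2 = 80 (one walk test and one treadmill test each).
- Visit 3 tests in controls: 13 × 2 = 26.
- In people with no program exposure: 80 + 26 = 106, and 106/160 = 66%.
- Visit 3 tests in arm 1, the only ones performed after program exposure: 27 × 2 = 54, or 34%.
- Tests in arm 1 whose later effects are first asked about after program exposure: the Visit 2 treadmill test and both Visit 3 tests, 27 × 3 = 81, or 51%.

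The two-thirds share follows from the design whatever the sample size: 1/2 + (1/2 × 1/3) = 2/3. Losses before Visit 3 in proportion to the arms would lower the count and raise the share. These are numbers of tests, not of events; the documents give no event rate and none is assumed.

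**The case against.** The strongest reply is that the field asks a narrow question and gets a true answer. A control injured on the treadmill was not injured by the step-goal program, so *Not Related* is correct. The category requires a documented cause, so the test would be named. Every event is recorded whatever its relationship, with a description and onset time, and falls and injuries are tracked daily. Prompt reporting of unanticipated problems and of serious and unexpected events does not depend on relatedness; since the protocol expects no serious events, a serious test injury would qualify. An independent committee reviews the data. The case report form is not among the documents, and the list of its items is not worded as exhaustive, so a procedure field may exist.

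All of that stands, and it limits the point to one of classification. It also rules out some stronger readings that a reader might infer:

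- *That procedure harm must be coded Not Related.* No rule says so; the study intervention is undefined, and the wording only points that way.
- *That test harm in arm 1 is bound to be confused with the program.* Immediate harm from baseline tests cannot reasonably be. The two strongest categories require other factors to be ruled out or judged unlikely. Confusion is possible, mainly for delayed or nonspecific complaints.
- *That the safety summary will undercount research-related harm.* The Analytical Plan specifies no adverse-event table, so no described output carries an undercount.
- *That only about a third of the tests, those in controls, fall outside program exposure.* This leaves out the baseline tests in arm 1.

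The reply does not remove the need to recover procedure harm from free text. Nor does it help with a complaint first elicited 12 weeks after the test.

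**Conclusion.** The point holds as a gap in safety classification. Relatedness and expectedness have a single reference point, narrower than the protocol's own definition of an adverse event, and the relatedness field cannot separate procedure harm from harm unconnected to the research. In arm 1, delayed or nonspecific effects of a test can be attributed to the program.

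At most about 106 of 160 exertional tests occur in people with no program exposure, and about 54 in people with it. This assumes full randomization and completion at about 27:13, and reads the study intervention as the step-goal program, as the protocol's own usage suggests.

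Recording of events, prompt reporting, the primary endpoints and the sample size are not affected. The change is worth making because it is cheap and because the results are meant to guide a larger trial.

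**What to change.** - State in the protocol that the study intervention means the step-goal program.
- Add a second relatedness field to the case report form, completed for all participants: related to a study procedure, specifying exercise test, 6-minute walk test or device. The Garmin is worn in both arms but is also a coaching tool in arm 1, so the form's instructions should say how to code events involving it.
- Treat an event as unrelated to the research only when it is independent of both the program and the procedures.
- Apply the same split to expectedness, with the risk information for the procedures set out alongside that for the program.
- Specify in the Analytical Plan a table of procedure-related and intervention-related events, shown separately and by arm.

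The cost is one extra field, some protocol wording and a small table. No visit, procedure or treatment changes. If the form already holds such a field, only the protocol text and the table are needed.
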